This study will use a 2 x 2 randomized design with all 100 post- menopausal subjects being randomized to metformin, placebo, placebo and intensive lifestyle intervention, or metformin and intensive lifestyle intervention. Treatments will last 4 months. Participants will be assessed at baseline and end of treatment with endometrial sampling to see if there are changes in the biomarkers.

Protocol Sections

1.0 Objectives

1.1 Primary Objectives

1.1.1 The primary objective of this study is to evaluate the independent effects of metformin and a diet and physical activity intervention on potential surrogate endpoint biomarkers (SEBs) of the endometrium in obese post-menopausal women. The SEBs includes the panel of genes listed in Table 1 in Section 2.6 and Ki-67 biomarker.

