9.0 Statistical Considerations

This is a partially blinded, randomized study to evaluate the effects of intervention upon Ki-67 and other biomarkers. Participants and researchers will be blinded with regard to assignment of study drug (placebo vs. metformin) but they will not be blinded with regard to assignment of lifestyle intervention. We will use a form of adaptive randomization called minimization, which is similar to stratification in that participant characteristics are used to assign them to the treatment conditions to achieve better group balance. Groups will be balanced with regard to age (50-65 years), BMI (Class I and II: 30.0-39.9 and Class III or greater: ≥ 40), and whether they meet current exercise guidelines as recommended by the Physical Activity Guidelines for Americans.

The primary objective of this study is to evaluate the effect of intervention (metformin and/or lifestyle intervention) on Ki-67. Secondary endpoints include examination of intervention on:

- (a) genes relevant to estrogen dependent endometrial proliferation, hyperplasia and cancer using Q-PCR (PCNA, sFRP4, RALDH2, IGF-1R, survivin, and EIG121),
- (b) biomarkers specific to the effect of metformin treatment (phospho-AMPKa, phospho-ACC, phospho-mTOR and phospho-S6 ribosomal protein).

Additionally, we will examine changes in serum levels of estradiol, estrone, testosterone, DHEA-S, sex hormone binding globulin (SHBG), adiponectin, glucose,

HbA1c, insulin and insulin-like growth factor-1 (IGF-1) and all biobehavioral outcomes, such as changes in body composition, physical activity, quality of life (QoL), diet, etc.

We will analyze differences in Ki-67 and other outcomes using 2x2 ANOVA models. If lifestyle intervention is found to affect change in Ki-67 expression or other outcomes, we will use the methods described by Baron and Kenney [78] to determine whether these changes were mediated by weight loss, body composition changes, physical activity changes, and dietary changes. Differences between arms with regard to adverse events and other toxicities will be examined using Fisher's exact tests. Changes from baseline lab values will be examined 2x2 ANOVA models.

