A study of Ki-67 change in participants at high risk for endometrial cancer (Lynch patients) indicated we could expect a mean decrease in Ki-67 of 3.5 (after log-transformation) in the Metformin alone group with a standard deviation of 0.8. For the purposes of estimating power, we assumed that the lifestyle intervention alone group would have the same mean and standard deviation decrease, but we halved mean decrease for our calculations to take into account the non-compliance we might observe in this group. Finally, we estimated power for a moderate interaction effect – half of the metformin intervention effect in addition to the additive effect of metformin and lifestyle intervention. Specifically, we calculated power assuming that the mean decreases in the control arm, metformin alone arm, lifestyle intervention alone arm and metformin plus lifestyle intervention arm were 0, 3.5, 1.75 and 7, respectively. Using a 2-sided test with 5% statistical significance, we will have over 95% power to detect these differences when the common standard deviation is 0.8. Additionally, we will still have adequate power to detect much smaller differences. For example, we will have 80% power to detect a lifestyle alone main effect of 0.3 and still have over 95% power to detect a metformin main effect and an interaction effect of 0.6 and 1.2, respectively, when the common standard deviation is 0.8. Power was calculated using PASS 2005 (copyright

© 2005, Jerry Hintze).

All testing will be 2-sided with 5% statistical significance. The primary efficacy analysis will be intent-to-treat. Patients who discontinue early from the study will be included in the analysis as not having a change from baseline values. Additionally, we will use the methods described by Benjamini and Hochberg [51] to control the false discovery rate in the secondary efficacy analyses.

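### Section 9.0 claims 80% power for a lifestyle effect of 0.3, but the design gives about 46% for it as a main effect and about 26% for lifestyle alone

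*Combined protocol and SAP*

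**What the plan says.** Section 1.1 sets the primary objective as to "evaluate the independent effects of metformin and a diet and physical activity intervention". It does not define independent. Section 9.0 words the objective as to "evaluate the effect of intervention (metformin and/or lifestyle intervention) on Ki-67" and names one analysis: "We will analyze differences in Ki-67 and other outcomes using 2x2 ANOVA models". It does not say which contrasts will be reported, or how a main effect is to be read if the two interventions interact.

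The power calculation in Section 9.0 assumes that mean "decreases in the control arm, metformin alone arm, lifestyle intervention alone arm and metformin plus lifestyle intervention arm were 0, 3.5, 1.75 and 7", in that order, on the log Ki-67 scale. The combined arm includes a synergy term, described as "half of the metformin intervention effect in addition to the additive effect of metformin and lifestyle intervention". For these means the section states that "we will have over 95% power to detect these differences when the common standard deviation is 0.8".

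The section then gives a second scenario with smaller effects and the same SD. It claims "80% power to detect a lifestyle alone main effect of 0.3", and over 95% power for a metformin main effect of 0.6 and an interaction effect of 1.2. Section 5.4 allocates 25 women to each of the four arms.

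**The concern.** The phrase in the second scenario joins two different quantities. An effect of lifestyle alone is a simple effect: lifestyle plus placebo against placebo without lifestyle, 25 v 25. A main effect is the average of the lifestyle effects with and without metformin, 50 v 50. The two agree only if there is no interaction, and the plan assumes one. They also have different standard errors, so one power figure cannot serve both.

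Two things are at stake. A reader would take it that the trial has 80% power for a lifestyle effect of 0.3 on the primary endpoint. And a lifestyle main effect could be reported as the effect of lifestyle alone although it came largely from the combination arm. A main effect of 0.45, for example, arises from lifestyle effects of 0.3 and 0.6 without and with metformin, and equally from 0 and 0.9.

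**Working it through.** **Inputs.** 25 per arm (Section 5.4). SD 0.8, two-sided 5%, and the planning means (all Section 9.0). Error degrees of freedom: 100 − 4 = 96. Power is from the noncentral F distribution with 1 and 96 df and noncentrality (effect/SE)².

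**Standard errors.**
- Main effect (50 v 50): 0.8 × √(2/50) = 0.16
- Simple effect (25 v 25): 0.8 × √(2/25) = 0.226
- Interaction (both − metformin − lifestyle + control): 0.8 × √(4/25) = 0.32

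**Step 1. Reproduce the headline claim (means 0, 3.5, 1.75, 7).**
- Metformin main effect: (3.5 + (7 − 1.75))/2 = (3.5 + 5.25)/2 = 4.375, power about 100%
- Lifestyle main effect: (1.75 + (7 − 3.5))/2 = (1.75 + 3.5)/2 = 2.625, power about 100%
- Interaction: 7 − 3.5 − 1.75 + 0 = 1.75, power 99.97%

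The stated figure of over 95% is reproduced. The simple effects of 3.5 and 1.75 against the double-control arm also have about 100% power.

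**Step 2. Compare main and simple effects in that scenario.** Metformin: 4.375/3.5 = 1.25, so +25%. Lifestyle: 2.625/1.75 = 1.50, so +50%. With an additive combined arm (3.5 + 1.75 = 5.25) both ratios are 1.00, so the gap comes entirely from the assumed synergy.

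**Step 3. Try to reproduce the smaller scenario.**

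| Reading of 0.3, 0.6, 1.2 | Lifestyle (stated 80%) | Metformin (stated over 95%) | Interaction (stated over 95%) |
|---|---|---|---|
| Literal: main effects 0.3 and 0.6, interaction contrast 1.2 | 45.9% | 96.0% | 96.0% |
| Cell means 0, 0.6, 0.3, 1.2 | 79.5% | 99.6% | 15.3% |
| Deviations of ±0.3 and ±0.6 (differences 0.6 and 1.2) | 96.0% | about 100% | not computed |

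Under the cell-mean reading the quantities tested are:
- lifestyle main effect (0.3 + (1.2 − 0.6))/2 = 0.45
- metformin main effect (0.6 + (1.2 − 0.3))/2 = 0.75
- interaction 1.2 − 0.6 − 0.3 = 0.3

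A one-sided test of a literal 0.3 does not rescue the 80% either: it gives 59.1% (normal approximation). The cell-mean reading is the only one tried that returns the 80%. It also keeps the pattern of the headline means: 0.3/0.6 = 1.75/3.5 = 0.5 and 1.2/0.6 = 7/3.5 = 2. But it contradicts the interaction claim. No reading tried gives all three stated figures.

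**Step 4. Power for each intervention alone, cell-mean reading (25 v 25).**
- Lifestyle alone, 0.3: 0.3/0.226, power 25.9%
- Metformin alone, 0.6: 0.6/0.226, power 74.7%

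For 80% power on a lifestyle-alone effect of 0.3, about 113 women per arm would be needed.

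**The case against.** The sponsor has a good case on the analysis itself. In a factorial trial the separate effect of each factor is commonly taken to be its main effect, and Section 9.0 words the objective broadly enough to cover that. A main effect is an unbiased estimate of the averaged effect; it is not a distorted estimate of the simple effect. The 25% and 50% gaps exist only if there is synergy, and the combined-arm mean of 7 is an assumption made for power. Section 9.0 also gives power for an interaction, so the model evidently includes that term, and simple effects can be drawn from it. In the headline scenario the interaction would almost certainly be detected. Resting every claim on 25 v 25 comparisons would give up the factorial's efficiency even where the effects are additive.

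All of this stands. A reader might infer from the 25% and 50% that the 2x2 ANOVA overstates the effects, or fails to answer the primary objective. The documents do not support that, because they leave independent undefined and the averaged effect is a legitimate target.

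None of it repairs the power sentence. Read literally, its lifestyle figure fails. Read as cell means, its interaction figure fails.

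**Conclusion.** The second power statement in Section 9.0 is wrong as written under every reading tried. For lifestyle at 0.3 the design has about 46% power as a main effect and about 26% as lifestyle alone, against a stated 80%. The 80% belongs to a lifestyle main effect of about 0.45. If that is how it was obtained, the matching interaction has about 15% power, not over 95%.

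The related point is one of interpretation. Under the planning synergy the main effects exceed the single-intervention effects by 25% for metformin and 50% for lifestyle. These are one value per intervention, not a range, and they are zero under additivity. The main effects are valid averages, but alone they cannot support a statement about either intervention by itself.

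A reader might also infer that the trial is too small for the effects it was planned on. It is not: the headline scenario reproduces, with about 100% power even for the simple effects.

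The figures assume 25 analysed women per arm, a common SD of 0.8 and no early discontinuation. Section 9.0 counts discontinuers as unchanged but gives no rate. At an equal rate in all arms this shrinks every mean effect alike and leaves the 25% and 50% as they are. That 0.3 is a cell mean is an inference from the arithmetic; the plan does not say so.

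**What to change.** In Section 9.0:

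1. Restate the smaller-effect power sentence with the exact contrast, its size and its power. For example, 80% power is for a lifestyle main effect of about 0.45 (50 v 50). If the cell means 0, 0.6, 0.3 and 1.2 were intended, list them and give the interaction as 0.3 with about 15% power. If 1.2 was meant as the interaction contrast itself, say so and correct the lifestyle figure to about 46%.
2. Keep the main effects as the 2x2 ANOVA result and describe them as averages over the other factor. Say whether independent in Section 1.1 has that meaning.
3. Beside them, report the interaction estimate and the four simple effects (each intervention within each level of the other) with 95% CIs, so that no claim about an intervention alone rests on the main effect only. Present these as supporting estimates, because the false discovery rate control in Section 9.0 covers only the secondary analyses.

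This needs no extra participants or data, only further contrasts from the same model and some rewording. The cost is wider intervals for the simple effects (SE 0.226 against 0.16) and a less favourable stated power.

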1.1.2 Other biomarkers will be examined, including

1.1.2.1 A panel of genes (PCNA, IGF-IR, RALDH2, sFRP4, survivin, and EIG121) relevant to estrogen-dependent endometrial proliferation, hyperplasia and cancer using Q-PCR.

1.1.2.2 Biomarkers specific to the effect of metformin treatment (phospho-AMPKa, phospho-ACC, phospho-mTOR and phospho-S6 ribosomal protein).

1.2 Endpoints

1.2.1 The primary endpoint biomarker that will be investigated is proliferation Ki-67.

1.2.2 Secondary endpoints include:

1.2.2.1 Changes in serum levels of estradiol, estrone, testosterone, DHEA-S, sex hormone binding globulin (SHBG), adiponectin, glucose (fasting), HbA1c, insulin (fasting) and insulin-like growth factor-1 (IGF-1).

1.2.2.2 Changes in diet, physical activity, body composition (BMI, waist and hip circumference, and measurements from the DEXA scan), quality of life, and psychosocial determinants of behavior change will be examined in this sample of obese, post-menopausal women taking metformin or receiving a diet and physical activity intervention.

2.0 Background

2.1 Obesity and endometrial cancer

Numerous epidemiologic studies have demonstrated that obesity is strongly associated with an increased risk of endometrial cancer. While an average woman has a 3% lifetime risk of endometrial cancer, obese women have a 9-10% lifetime risk of endometrial cancer.[1] In addition, obese women account for almost 50% of all endometrial cancers.[1] In a recent review of diet and cancer by the American Institute for Cancer Research and World Cancer Research Fund (WCRF), authors stated that the evidence relating body mass index and cancer is strongest for endometrial cancer, but also is compelling for breast, colon, kidney and gallbladder cancer.[2]

There are a number of ways in which obesity has been hypothesized to increase risk of endometrial cancer. Obese women have increased bioavailability of adrenal steroids, increased peripheral conversion in adipose tissues of the adrenal steroids to estrone, and increased bioavailability of free estrogens due to decreased sex hormone binding globulin. This “hyper-estrogenic state” is believed to result in increased endometrial cell mitosis, leading to endometrial hyperplasia, a pre- malignant lesion, and to endometrial cancer. However, increased levels of circulating endogenous estrogen cannot completely explain the association of obesity and endometrial cancer. While some clinical studies show a correlation between higher plasma levels of endogenous estrogens or androgens in women with endometrial cancer versus controls, others do not.[3-13] Epidemiologic studies addressing this question also yield conflicting results. In a large study by Potischman et al, the authors found that body mass index remained a significant risk factor for the development of endometrial cancer even after controlling for endogenous estrogen. They concluded that high levels of endogenous estrogens were not sufficient to explain the increased risk of obesity to endometrial cancer.[11] Another prospective multicenter study demonstrated that the risk of endometrial cancer associated with endogenous estrogen levels in postmenopausal women remained significant after adjusting for BMI.[13]

What other mechanisms could explain the association of obesity to the development of endometrial cancer? Are there other mechanisms that explain why obesity is associated with a number of other cancers? The American Cancer Society has recently highlighted the increased risk of a number of cancers in obese women. In particular, cancers of hormonally regulated organs, including endometrium, breast and ovary, have been shown in epidemiologic studies to be associated with obesity.[14]

Other cancers including gallbladder, colon and prostate are also seen more frequently in the obese.[14] Is there an underlying metabolic cause for this increased cancer risk?

Hyperinsulinemia and the insulin resistant state are closely associated with obesity, and may contribute in a meaningful way to increase the risk of cancer in an obese person. Recently, adiponectin, an adipocyte- derived protein highly correlated with hyperinsulinemia, has been shown to be associated with endometrial cancer, independent of body mass index.[15, 16] One study has demonstrated that this association between adiponectin and endometrial cancer may be stronger in postmenopausal women than premenopausal women.[16] Studies in patients with diabetes have demonstrated varying effects of metformin on serum levels of adiponectin.[17, 18]

Furthermore, since insulin has been shown to potentiate estrogen-regulated gene expression, obese women in particular may be at increased risk for estrogen associated cancers, including endometrial cancer. Epidemiologically, a number of studies have shown a modest association of diabetes with endometrial cancer risk.[19-24] Interestingly, in three studies the most significant risks were seen in women who were both obese and diabetic.[19, 22, 24] A study by Troisi et al examined insulin levels in women with endometrial cancer compared to controls in order to determine if elevated insulin levels could explain the association of obesity and endometrial cancer.[25] While elevated serum insulin levels, as measured by C-protein, were associated with increased risk of endometrial cancer, elevation of serum insulin levels *alone* could not account for the association of obesity and endometrial cancer. In this study we will address the hypothesis that obesity associated hyperinsulinemia and insulin resistance, in combination with hyperestrogenism, contributes to the increased risk of endometrial cancer.

2.2 Metformin, mechanism of action and possible role in the prevention of cancer

While metformin was first described more than 50 years ago, the exact molecular mechanism of action for this drug has only recently been determined.[26] Metformin activates AMP-activated protein kinase (AMPK) via phosphorylation by the LKB1 tumor suppressor.[27, 28] AMPK is typically activated in response to metabolic stress, and results in inhibition of ATP-consuming pathways, such as cholesterol synthesis, fatty acid synthesis and protein translation.[29, 30] Importantly, AMPK inhibits mTOR via phosphorylation and activation of tuberous sclerosis complex 2 (TSC2). TSC1/TSC2 forms the TSC complex that negatively regulates mTOR signaling.[31]

Recent clinical studies suggest that metformin may be associated with a decreased risk of cancer. In an observational cohort study of diabetics performed by Libby et al, incident cancer was diagnosed among 7.3% of 4,085 metformin users compared with 11.6% of 4,085 comparators ($p<0.001$).[32] In a recent case-control study performed at MD Anderson, Li et al reported that diabetic patients who had taken metformin had a significantly lower risk of pancreatic cancer compared to those who had not taken metformin.[33] Jiralerspong et al reported that among diabetic women with breast

cancer undergoing neoadjuvant chemotherapy, those individuals who were on metformin had a higher pathologic complete response rate than those who were on other anti-diabetic medication.[34] The results of these studies are provocative, and suggest that metformin may have a role in both the prevention and treatment of multiple cancers.

The signaling pathways activated by metformin treatment suggest a promising role for metformin as an anti-cancer agent in endometrial cancer, as well as other cancers that have activated PIK3CA/AKT/mTOR pathways. Metformin treatment in estradiol treated Balb/c mice resulted in significantly decreased density of endometrial glands, decreased immunohistochemical expression of mTOR signaling and decreased proliferation indices as measured by PCNA expression.[35] Ben Sahra et al investigated the effects of metformin on human prostate cancer cells (LNCaP) and in an *in vivo* xenograft mouse model. Their studies identified that in LNCaP cancer cells metformin activated AMPK and inhibited proliferation by blocking the cell cycle in G0/G1 phase, which was accompanied by decreased cyclin D1, decreased phosphorylation of Rb and increased p27Kip1 expression. Metformin treatment of an LNCaP tumor bearing xenograft model resulted in a significant reduction in tumor growth.[36] Schneider et al. investigated the effect of metformin in high-fat diet fed hamsters; a model of pancreatic cancer. They identified that 50% of the high-fat diet fed hamsters develop pancreatic tumors; whereas metformin treated high-fat diet fed hamsters did not develop tumors.[37] Additionally, administration of metformin to LKB1 hypomorphic PTEN^{+/−} mice increased AMPK phosphorylation and significantly delayed tumor onset with 100% of the control group developing tumors of the liver, spleen and intestine by 4 months of age and the metformin treated group developing tumors by 5 months of age.[38] Taken together, these studies suggest that metformin may prevent or significantly delay tumor progression as a consequence of AMPK activation.

The effect of metformin on the endometrium has been examined in women with polycystic ovarian syndrome. In a small, open-label study of metformin versus rosiglitazone, endometrial histology was evaluated at baseline and following a 3- month treatment period in 16 women with PCOS. Two women with simple hyperplasia were treated with metformin and experienced regression during treatment providing preliminary evidence that metformin may have beneficial effects on the endometrium.[39] The results of this study, in addition to our studies in rodents, provide evidence that metformin has a direct effect on the endometrium.

2.3 Diet and exercise linked to hyperinsulinemia and insulin resistance

The landmark Diabetes Prevention Program (DPP) trial compared a lifestyle intervention or metformin to metformin placebo. The intensive portion of the lifestyle intervention was composed of 16 face-to-face sessions with a lifestyle coach in which participants were assisted with increasing their physical activity, reducing their caloric intake, and reducing weight by at least 7%. The trial demonstrated that both a lifestyle intervention and metformin reduced incidence of diabetes, with larger effects for the lifestyle intervention [22]. **Particularly notable given the relationship between**

endometrial cancer and adiponectin was that both interventions were associated with increases in adiponectin, with the effects of the lifestyle intervention being approximately 3.5 times larger than those for the metformin group [23]. Lifestyle intervention and metformin were also associated with reductions in metabolic syndrome [24] and (C-reactive protein) CRP in women, the reduction in CRP was related to weight loss [25]. The effects of the lifestyle intervention on adiponectin may be related primarily to weight loss; a small study found that reduced calorie diet with or without exercise increased circulating adiponectin, but that exercise alone and exercise plus reduced calorie diet enhanced expression of adiponectin receptors in skeletal muscle and adipose tissue [26]. Increases in adiponectin also have been found in response to weight loss after bariatric surgery [27]. Interestingly, in a recent report on the association of bariatric surgery and cancer incidence, the disease most profoundly affected was uterine cancer, primarily EndoCa [28].

We are intrigued by the possibility that both pharmacologic intervention with metformin and a lifestyle behavior intervention, both of which reduce insulin resistance, might also have a direct chemopreventive effect of EC. Currently, options for EC chemoprevention include use of the oral contraceptive or use of progestins.[40] Both have limitations in an obese cohort. Oral contraceptives (OCP) are contraindicated in morbidly obese individuals due to an increase in rate of thrombo-embolic events. In addition, obese women frequently have hypertension or hypercholesterolemia, which are also considered contraindications to OCP use. Progestins have similar contraindications and compound obesity by stimulating appetite. While weight loss and exercise are obvious solutions to decreasing the risk of EC in obese individuals, exploration of alternative approaches is necessary. The novelty of these chemoprevention/behavioral prevention strategy is twofold. First, it proposes to treat an underlying metabolic syndrome. Rather than focusing on the prevention of a single cancer, this strategy may have not only had an overall benefit for the cardiovascular health of the obese woman but may also decrease the risk of endometrial, pancreatic and perhaps other cancers associated with obesity and insulin resistance.[33] Second, it exploits the newly identified function of metformin as a drug that demonstrates direct anti-proliferative effects on endometrial (and other) cells via activation of AMPK and inhibition of mTOR.

